### Schedule of events:

### 3.4 Study Endpoints

#### 3.4.1 Primary Study Endpoint

The primary endpoint for this study will be case completion rate without alternative mode of oxygenation. In other words, for each case, the ability to complete the surgical procedure with use of only Hi-VNI device for oxygenation will be assessed.

#### 3.4.2 Secondary Study Endpoints

The secondary endpoints for the study will be the total case duration (induction to end of surgery), the time from the end of the case to emergence from anesthesia, nadir SpO2, peak TcpCO2, and rate of change in TcpCO2 (transcutaneous CO2).

## 4 Study Population and Duration of Participation

### 4.1 Duration of Study Participation

The subject's participation in this study will be limited to the time of their upper airway surgery and the time needed for post-operative recovery. No long-term follow-up will be conducted for this study.

## **4.2 Total Number of Subjects and Sites**

We estimate that 100 subjects will be recruited for this study. Penn will be the only study site.

## **4.3 Inclusion Criteria**

Our study population will include adult patients (22 years old or older) who are scheduled to undergo upper airway surgery at our institution with the airway pathology that will require surgical interventions which could potentially benefit from a tubeless surgical field. The airway pathology located directly at the site of the endotracheal tube placement (supraglottis, glottis, subglottis, and proximal trachea) will benefit from a tubeless surgical field.

- Patients must be able to read and understand English
- Participants must sign the informed consent form
- The surgical case must be a scheduled elective case and not performed as an urgent or emergent case

## **4.4 Exclusion Criteria**

All patients with underlying medical conditions in which periods of hypoxemia or hypercarbia are not well tolerated will be excluded. Patients in whom delivery of air with oxygen via nasal passages is contraindicated will be excluded. The manufacturer's guidelines for Hi-VNI device use will be followed. The exclusion criteria will be defined as follows:

- Pregnancy (at our institution, all female patients of childbearing age receive a pregnancy test clinically prior to surgery as part of SOC)
- Coronary artery disease or carotid/vertebral artery stenosis
- Severe heart failure with EF < 20% or implanted ICD
- Pulmonary hypertension or pulmonary fibrosis
- History of increased intracranial pressure
- History of skull base or intracranial surgery
- Severe nasal obstruction
- Extremely low or extremely high BMI (BMI < 16 kg/m^2 or BMI > 40 kg/m^2)
- Baseline home O2 or Baseline SpO2 < 90%
- Airway pathology requiring laser use for surgical management
- Airway pathology requiring surgical intervention with high risk of large-volume bleeding
- Airway pathology requiring use of cautery throughout the procedure
- High risk of aspiration during the procedure as determined by the patient evaluation and review of prior medical history (history of gastrointestinal obstruction, prior esophageal procedures, esophageal cancer, hiatal hernia, incoordination of swallowing and respiration, class III obesity defined as BMI>40)
- Patients who are taken to the OR for an urgent or emergent upper airway surgery

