## Study Summary

Title	High Velocity Nasal Insufflation (Hi-VNI) Use in Upper Airway Surgery
Short Title	Hi-VNI Use in Upper Airway Surgery
IRB Number	834412
Methodology	Prospective, interventional, pilot study
Study Duration	1 year
Study Center	Single center (University of Pennsylvania)
Objectives	

• To establish the efficacy of Hi-VNI in upper airway surgery from the anesthesiologist's and surgeon's perspectives

• To describe the ideal patient and the ideal pathology as well as suitable clinical scenarios when Hi-VNI should be selected

Number of Subjects	100
Main Inclusion and Exclusion Criteria	
Inclusion criteria: Adult patients who are scheduled to undergo elective upper airway surgery at Penn.
 
Exclusion criteria: All patients with underlying medical conditions in which brief periods of hypoxemia or hypercarbia are not well tolerated will be excluded. Patients in whom delivery of air with oxygen via nasal passages is contraindicated will be excluded.
 

• Coronary artery disease

• Severe heart failure with EF < 40% or implanted ICD

• Pulmonary hypertension or pulmonary fibrosis

• History of increased intracranial pressure

• History of skull base or intracranial surgery

• Severe nasal obstruction

• Extremely low or extremely high BMI (BMI <16 or >40)

• Patients at high risk for aspiration

• Patients taken to OR for urgent or emergent upper airway surgery

Intervention	This study will involve use of Hi-VNI device as a primary or adjunct method for oxygenation.
Statistical Methodology	Mann-Whitney U test or Student's t-test and Kruskal-Wallis or ANOVA test will be used depending on the data distribution and the number of variables.
Data and Safety Monitoring Plan	The PI and sub-Is for this study will be responsible for the safety of the subjects enrolled into this study.

CONFIDENTIAL

This material is the property of the University of Pennsylvania.

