#### **5.1 Screening**

The PI will identify eligible participants for this study using the surgical schedule and/or clinic schedule. The subject's eligibility will be determined based on the type of the airway pathology, the type of planned surgical procedure and the exclusion criteria already described in Section 4.4 of this protocol. Additionally, the anesthesia team will make sure at the beginning of each case that adequate mask ventilation can be performed on each patient who consents to participate in the procedure to ensure that during the procedure the anesthesia team can safely switch to alternate modes of oxygenation.

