### **5.4 Subject Withdrawal**

All study subjects may withdraw from the study at any time without impact to their care. They may also be discontinued from the study at the discretion of the PI and co-Is if it is determined that they are not good candidates for Hi-VNI use immediately prior to surgical procedure or during the surgical procedure. This decision will be made based on a joint discussion between the airway surgeon and the anesthesiologist.

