## **6.3 Control of Bias and Confounding**

This is an interventional study that will involve recruitment of subjects who are scheduled to undergo an upper airway surgery and are good candidates for use of Hi-VNI during their procedure. The investigators for this study expect some degree of bias during the subject recruitment phase, but this selection bias will help exclude patients who will not tolerate use of Hi-VNI for oxygenation during surgery due to their co-morbidities. Please see Section 4.4 for exclusion criteria defined for this study.

CONFIDENTIAL

This material is the property of the University of Pennsylvania.

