## **10 Ethical Considerations**

All study team members have experience/training in clinical research and have completed their CITI human subjects training. All study team members will be asked to document their role on the study delegation log. Ongoing training will take place as needed. The investigators will maintain open communication with study staff and IRB, and will submit protocol changes to IRB for approval prior to implementing them.

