Patients who are not candidates for Hi-VNI use will be excluded from this study. These patients include those with underlying medical conditions in which brief periods of hypoxemia or hypercarbia are not well-tolerated, such as pregnant patients, patients with coronary artery disease or carotid/vertebral artery stenosis, patients with severe heart failure or implanted ICD, patients with extremely low or extremely high BMI or patients with baseline hypoxia and oxygen requirement at home. Additionally, patients in whom use of high-flow oxygenation is contraindicated, such as patients with increased intracranial pressure or history of skull base surgery, will be excluded. Patients at high risk for aspiration and patients scheduled for emergent or urgent interventions will also be excluded.

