## **10.3 Risk Benefit Assessment**

The Risk Benefit Assessment will be done for each individual subject before proceeding with the enrollment to ensure that use of Hi-VNI during upper airway surgery does not predispose the potential subject to any foreseeable harm or risk of complications. This assessment will involve a joint discussion between the airway surgeon (the PI) and the anesthesiologist (the sub-Is).

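### The ejection-fraction cut-off for excluding severe heart failure is 40% in the Study Summary but 20% in section 4.4, the list used for screening

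*Combined protocol and SAP*

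**What the plan says.** The heart-failure exclusion appears in three places in the combined protocol and SAP.

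- **Section 4.4 (Exclusion Criteria):** "Severe heart failure with EF < 20% or implanted ICD".
- **Study Summary (main inclusion and exclusion criteria):** the same item, with the EF limit and ICD clause reading "40% or implanted ICD".
- **Section 10.1 (Risks):** "patients with severe heart failure or implanted ICD", with no EF figure.

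Two other sections say which list governs. Section 5.1 (Screening) bases eligibility on the pathology, the planned procedure and "the exclusion criteria already described in Section 4.4 of this protocol". Section 6.3 (Control of Bias and Confounding) adds "Please see Section 4.4 for exclusion criteria defined for this study".

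Section 4.4 also opens with a general exclusion, carrying no number, for conditions that make low oxygen or high carbon dioxide poorly tolerated.

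**The concern.** The two cut-offs cannot both be right, and the looser one sits in the section that screening uses.

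This is a safety exclusion. Section 10.1 lists severe heart failure among the conditions in which short spells of hypoxemia or hypercarbia are badly tolerated, and the plan expects raised carbon dioxide to be common. Section 6.1 projects an end-of-procedure TcpCO2 of 57.75 to 67.88 mmHg against a switch threshold of 55 mmHg (after subtracting the baseline gradient). It concludes that only about 16% of patients will avoid a change to another mode of ventilation.

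Two things are at stake. A patient whom the Summary would keep out for safety could be enrolled under 4.4. And an IRB or auditor could not say from the text whether enrolling a patient with severe heart failure and an EF of, say, 30% is a protocol deviation. Section 7.5.2 provides no formal safety monitoring committee, so the written eligibility limits carry more weight.

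**Working it through.** No power or sample-size formula bears on this point. The check sets the texts side by side and asks which patients are treated differently.

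**1. Is the difference just abridgement?** The Summary is headed as listing the main criteria, which would explain items left out. It would not explain a changed number. The numerical exclusion cut-offs that the Summary repeats are:

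| Cut-off | Study Summary | Section 4.4 | Match |
|---|---|---|---|
| EF, severe heart failure | below 40% | below 20% | No |
| BMI, lower limit | below 16 | below 16 | Yes |
| BMI, upper limit | above 40 | above 40 | Yes |

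Two of the three agree; only EF differs.

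**2. Who is affected?** Take patients with severe heart failure and no other exclusion, and apply the heart-failure item from each place:

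| Patient | Study Summary | Section 4.4 item |
|---|---|---|
| EF below 20% | excluded | excluded |
| EF 20% to just under 40%, no ICD | excluded | **not excluded** |
| EF 20% to just under 40%, ICD | excluded | excluded |
| EF 40% or above, no ICD | not excluded | not excluded |

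Only the second row is in dispute. Its width is 40 − 20 = 20 percentage points of EF.

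**3. Which rule will be followed?** Section 4.4 presents its list as the definition of the exclusion criteria, and sections 5.1 and 6.3 both refer to it. A screener following the protocol therefore applies 20%.

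**4. Does any other text settle the number?** No. Section 10.1 names severe heart failure without an EF value. The opening clause of 4.4 has no number either. Section 10.3 states that "The Risk Benefit Assessment will be done for each individual subject before proceeding with the enrollment", and section 5.4 lets the team discontinue subjects found to be "not good candidates for Hi-VNI use immediately prior to surgical procedure or during the surgical procedure". Both rely on clinical judgement and give no EF limit.

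**5. How many patients?** The documents give neither a heart-failure frequency nor an EF distribution, so no estimate is possible. For scale only: 1% of the 100 planned subjects is 0.01 × 100 = 1 patient.

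**The case against.** The best defence accepts the mismatch and disputes its consequence.

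- **The governing rule is clear.** Section 4.4 defines the criteria and screening refers to it, so the stray number is in a synopsis. This is correct about which rule is applied. It does not help on safety, because the rule applied is the looser one, and it does not show that 20% was intended.
- **Section 10.1 already excludes the disputed group.** Read literally, it keeps out everyone with severe heart failure, whatever the EF, and the opening clause of 4.4 is mandatory. This has some force. But 10.1 can equally be read as shorthand for the 4.4 list, and 4.4 follows its general clause with the list that defines it. The reading lowers the risk without removing the conflict.
- **Clinical safeguards catch these patients.** Records review, preoperative evaluation, the joint risk-benefit discussion and discretionary discontinuation all reduce the practical risk. Coronary disease, pulmonary hypertension, home oxygen and a baseline SpO2 below 90% are excluded separately. This stands as mitigation, but none of these measures supplies an EF cut-off.
- **Nothing in the documents favours 40%.** Section 4.4 is the fuller list, so the Summary may be the outdated text and 20% deliberate. This also stands. It is why 40% should be a default that the investigators can displace with a stated reason.

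**Conclusion.** The concern holds. One of the two stated EF limits is wrong as written, and the less protective one governs screening. The inconsistency spans 20 percentage points of EF and affects patients with severe heart failure, no ICD and no other exclusion. How many such patients would present is unknown and may be few.

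The conclusion rests on reading both statements as current versions of the same criterion. They share the same wording apart from the number, and neither comes from an amendment log. It assumes nothing about which value the investigators meant.

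This needs correcting despite the possibly small numbers, because a safety exclusion has to have a single value.

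**What to change.** Amend the protocol so that one EF cut-off appears in both the Study Summary and section 4.4. Use EF below 40% in 4.4 unless the investigators confirm that 20% was intended and justify it to the IRB; in that case, correct the Summary. Adding the chosen number to section 10.1 is optional but would remove the remaining ambiguity. If enrolment has already begun, check the EF of any patient with severe heart failure enrolled under 4.4.

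The cost is a one-line change by the route in section 10, where the investigators "will submit protocol changes to IRB for approval prior to implementing them". The planned sample size, endpoint and analysis are unaffected. The one drawback of 40% is that a few otherwise eligible patients may be excluded.

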#### **4.5 Subject Recruitment**

Potential study participants will be identified using the surgical schedule and/or clinic schedule, and will be invited to participate using a standard informed consent form. Consent will be obtained by an Investigator (physician). Privacy will be ensured by discussing the study and the patient's disease within a private room in the clinic or in the pre-operative unit area, where they are unlikely to be overheard. Patients will be given ample time to read the consent form, discuss the study, ask questions, consider participation, and make an informed decision.

All potential participants will be provided with a short description of the Hi-VNI technique and the reasons for use of this technique during their surgical procedure. The subjects will have an opportunity to ask their airway surgeon (the PI) and their anesthesiologist (the sub-Is) about the reasons for selection of this airway management technique and any potential alternatives as well as the risks and benefits of its use during their airway procedure. The subjects will be enrolled into the study only after their consent is obtained and all of their questions about Hi-VNI have been answered.

#### **4.6 Vulnerable Populations**

There are no children or adolescents in this study, and all adult subjects will be competent to give consent. Negative pregnancy test (administered clinically, per standard of care) is one of the requirements for all adult female patients of reproductive age who are scheduled for surgical procedure at our institution, and pregnant women will be excluded from this study. Although not directly targeted, mentally disabled persons, economically or educationally disadvantaged persons, and/or employees or students of the University of Pennsylvania will not be denied enrollment and any special protections and/or additional safeguards will be undertaken in order to protect the rights and welfare of these subjects from coercion or undue influence as appropriate.

### **5 Study Procedures**

Please see section 3.3.

#### **5.1 Screening**

The PI will identify eligible participants for this study using the surgical schedule and/or clinic schedule. The subject's eligibility will be determined based on the type of the airway pathology, the type of planned surgical procedure and the exclusion criteria already described in Section 4.4 of this protocol. Additionally, the anesthesia team will make sure at the beginning of each case that adequate mask ventilation can be performed on each patient who consents to participate in the procedure to ensure that during the procedure the anesthesia team can safely switch to alternate modes of oxygenation.

#### **5.2 Study Intervention Phase**

All information needed for this study will be recorded during the upper airway surgical procedure and immediately after the surgical procedure in the post-operative recovery unit. Recruited subjects will not be followed long-term.

CONFIDENTIAL

This material is the property of the University of Pennsylvania.

### **5.3 Device Management**

There are two Precision Flow Hi-VNI devices in the PCAM equipment storage room. The surgical procedures planned for this study will be performed at PCAM. These devices will be stored according to the manufacturer's requirements and in compliance with the Penn peri-op policies for storage of standard anesthesia and peri-op equipment. No special storage or processing will be required when these devices are used for our research study. The devices will be used by fully-trained personnel, as the PI, co-Is, and research staff, as well as anesthesia support staff, had an in-service with the manufacturer's representative to learn how to use these devices. Disposable parts needed for the devices will be discarded after one use. All disposables will be provided by the manufacturer, Vapotherm, Inc.

### **5.4 Subject Withdrawal**

All study subjects may withdraw from the study at any time without impact to their care. They may also be discontinued from the study at the discretion of the PI and co-Is if it is determined that they are not good candidates for Hi-VNI use immediately prior to surgical procedure or during the surgical procedure. This decision will be made based on a joint discussion between the airway surgeon and the anesthesiologist.

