We intend to de-nitrogenate in the standard fashion with a face-mask. All patients will receive preoxygenation with bag-mask to ensure mask ventilation can be performed successfully during the case if needed and to determine end-tidal CO2. All patients who are successfully bag-masked during the induction phase will have disposable nasal cannula prongs placed to proceed with Hi-VNI use after the induction and the trial of bag-masking. If mask ventilation during the induction phase is successful, the anesthesia team will proceed with oxygenation via Hi-VNI device at a maximum rate of flow of 40 L/min and FiO2 of 100%. The rate of flow will remain at the maximum setting of 40 L/min throughout the case, and will not be adjusted at any point. If mask ventilation during the induction phase is unsuccessful, the anesthesia team will intubate the patient or HFJV will be initiated after exposure of the glottis by the airway surgeon as currently practiced, and this patient will be excluded from the study.

Transcutaneous CO2 is ideal for monitoring during apneic procedures with Hi-VNI since it provides a continuous trend of CO2 level and does not require a closed system (such as vent circuit attached to the endotracheal tube or a mask device). Prior studies reported no difference between transcutaneous CO2 levels and arterial CO2 levels during apneic procedures on the upper airway with Hi-VNI use and when the correlation between arterial and transcutaneous CO2 was measured in healthy volunteers. Transcutaneous CO2 correlated with arterial CO2 irrespective of BMI or sensor position further supporting its use in our study. Since the measurement of the transcutaneous O2 is still considered experimental, and its correlation with the patient's oxygenation state has not been described in the literature, we will not use this parameter in our study. Based on our initial clinical experience and the experience of our colleagues at other institutions with TcpCO2 monitor use during general

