anesthesia, it is evident that end-tidal CO2 deviates from the level of TcpCO2 measured by the TcpCO2 monitor. We plan to establish a gradient between the value of end-tidal CO2 and the value of TcpCO2 in the beginning of each case, while the patient is being pre-oxygenated with a bag-mask. This baseline gradient will be used to determine the level of TcpCO2 adequate for continuous use of Hi-VNI during the case.

The Hi-VNI device will be used during the surgical procedure with continuous monitoring by anesthesia team. If at any point the SpO2 drops below 90% or TpCO2 minus the baseline gradient value rises above 55 mmHg, the airway surgeon and the anesthesiologist will stop the procedure and immediately switch to an alternate means of oxygenation by placing an HFJV cannula or a small-sized endotracheal tube through the laryngoscope into the glottis/trachea (a step performed in the beginning of the case if HFJV or endotracheal intubation are selected as primary methods of oxygenation during the case). These levels of TcpCO2 were not previously correlated clinically with PaCO2, and therefore should be avoided when using Hi-VNI system.

A total of 5 breaths will be administered via the endotracheal tube to determine the ETCO2 reading. If the ETCO2 reading is above 60 mmHg, the patient will be ventilated via the endotracheal tube. In other words, continuous monitoring will ensure that clinically significant hypoxia or hypercarbia (defined as SpO2 level below 90% or ETCO2 levels above 60 mmHg) that could eventually lead to adverse events if not promptly corrected will always be avoided by immediate switch to alternate means of oxygenation. HFJV equipment, a small-sized endotracheal tube, and all standard operating room airway and resuscitation equipment will be available as is the current standard during each case to allow for safe use of Hi-VNI and to prepare for the cases in which alternate means of oxygenation may be required.

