All precautions will be taken to prevent vital sign changes that affect the accuracy of TcpCO2 measurements including changes in blood pressure, abnormal heart rhythm, or body temperature changes. Warming blankets will be used to avoid hypothermia. If a patient develops a transient arrhythmia or hypotension requiring vasopressor administration during the procedure, which can cause erroneous SpO2 and inaccurate TcpCO2, the patient will be intubated and the procedure will be completed with oxygenation/ventilation via the endotracheal tube. If the procedure cannot be performed with the endotracheal tube in place, the procedure will be aborted. If the arrhythmia persists, or if the nature of the arrhythmia is considered to warrant procedure termination, the procedure will be aborted. Additionally, if use of Hi-VNI support extends beyond 20 minutes, a blood sample will be drawn to evaluate CO2 level (PaCO2 or PvCO2). If the blood sample collection cannot be done, the patient will be intubated and ETCO2 will be measured.

[figure not shown]
If at any point during the procedure, a bleeding is encountered that requires cautery, the team will switch to an endotracheal tube to prevent aspiration of blood into the airway and to allow for appropriate hemostasis with use of cautery. If at any point during the procedure, it will become evident that the laser use is necessary, the team will switch to an alternate means of oxygenation. Standard practices currently in place to avoid airway fire will be used if the case demands use of electrocautery or laser. These practices will be implemented immediately once it becomes evident that either laser or electrocautery will be used. If laser or electrocautery will be used to control the bleeding during the case, following an endotracheal

[figure not shown]
intubation, appropriate washout of residual oxygen will take place per routine protocol, and the laser or cautery will not be used until FiO2 levels reach the values below 21%. All standard fire precautions will be used and the oropharynx will be suctioned to remove any potential residual oxygen excess. All cases will be screened prior to enrollment into the study to avoid inclusion of the cases with high risk of large-volume bleeding requiring cautery or with a need for laser use during the procedure.

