#### **5.4.1 Data Collection and Follow-up for Withdrawn Subjects**

Subjects who choose to withdraw from the study or will be withdrawn from the study at the discretion of the PI or co-I will not require any additional follow-up data collection for this study.

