If at any point during the procedure, a bleeding is encountered that requires cautery, the team will switch to an endotracheal tube to prevent aspiration of blood into the airway and to allow for appropriate hemostasis with use of cautery. If at any point during the procedure, it will become evident that the laser use is necessary, the team will switch to an alternate means of oxygenation. Standard practices currently in place to avoid airway fire will be used if the case demands use of electrocautery or laser. These practices will be implemented immediately once it becomes evident that either laser or electrocautery will be used. If laser or electrocautery will be used to control the bleeding during the case, following an endotracheal intubation, appropriate washout of residual oxygen will take place per routine protocol, and the laser or cautery will not be used until FiO2 levels reach the values below 21%. All standard fire precautions will be used and the oropharynx will be suctioned to remove any potential residual oxygen excess. All cases will be screened prior to enrollment into the study to avoid inclusion of the cases with high risk of large-volume bleeding requiring cautery or with a need for laser use during the procedure.

Any upper airway procedure we perform begins with direct laryngoscopy and the exposure of the glottic airway with a laryngoscope. With the exposed view of the vocal cords/glottic opening, the exchange step of endotracheal intubation or placement of the HFJV cannula takes a few seconds. The surgical and anesthesia staff assigned to these cases are familiar with the exchange from one mode of oxygenation to another since this is commonly performed for these cases. After performing a portion or the entire case with HFJV, the team then elect to intubate the patient for the final steps of the surgical case or for emergence from

anesthesia. In cases where HVNI is used the surgeon and anesthesiologist team will then decide if the patient will continue to receive oxygenation through the nasal cannula, get mask ventilated or get intubated. Investigators for this study do not anticipate any additional risks to the patient or significant additional time needed to complete these procedures during this study, even in the cases where use of Hi-VNI alone is insufficient.

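### Subjects can be discontinued from the study during surgery, and no visible text keeps them in the completion-rate denominator

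*Combined protocol and SAP*

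**What the plan says.** Section 3.4.1 makes the primary endpoint the rate of cases completed with no oxygenation mode other than Hi-VNI, judged case by case. The protocol describes three kinds of event that prevent or end Hi-VNI use.

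- **Before the start (3.3).** Cannula prongs are placed once mask ventilation has succeeded, "to proceed with Hi-VNI use after the induction and the trial of bag-masking". If mask ventilation fails, the patient is intubated or jet-ventilated, "and this patient will be excluded from the study". Section 10.1 describes the same patient as withdrawn.
- **Mandated switches after the start (3.3 and 10.1).** At the SpO2 or TcpCO2 limit, "the airway surgeon and the anesthesiologist will stop the procedure and immediately switch to an alternate means of oxygenation". With arrhythmia, or hypotension that needs a vasopressor, "the patient will be intubated and the procedure will be completed with oxygenation/ventilation via the endotracheal tube". With bleeding that needs cautery, "the team will switch to an endotracheal tube to prevent aspiration of blood into the airway". None of these rules says that the subject leaves the study.
- **Discretionary discontinuation (5.4).** The investigators may discontinue a subject from the study "if it is determined that they are not good candidates for Hi-VNI use immediately prior to surgical procedure or during the surgical procedure". The only stated basis is procedural: "This decision will be made based on a joint discussion between the airway surgeon and the anesthesiologist". Under 5.4.1 these subjects "will not require any additional follow-up data collection for this study".

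On analysis, 6.2 says that proportions are shown as counts and percentages, 6.3.2 speaks of averages and standard deviations, and 6.3 discusses bias only at recruitment. No analysis set is named. Section 6.1 adds 14 patients to a calculated 86. The addition covers two groups together: people who decline consent, and people who need another oxygenation mode for other reasons once Hi-VNI has been used.

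**The concern.** The study is open and single-arm, and the team running the case decides on discontinuation. If that decision comes after Hi-VNI has started, it can depend on how well Hi-VNI is working, which is what the endpoint measures. Section 5.4 gives no criterion that separates a discontinuation from a mandated switch, so the same failing case could be recorded as a counted non-completion or as a subject who left the study.

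The allowance in 6.1 adds to the doubt. Needing another mode after Hi-VNI has been used is failure on the primary endpoint, but the sentence treats it as a loss to be made up by recruitment.

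Two results are at stake: the completion rate itself, and the description of which patients and pathologies suit Hi-VNI. Unsuccessful cases would be missing from both.

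**Working it through.** **1. The plan's own figure.** Inputs from 6.1: rate 16%, 95% confidence, margin 5 points, 144 qualifying cases a year.

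n0 = 1.96² × 0.16 × 0.84 / 0.05² = 206.5

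With a finite population correction: 206.5 / (1 + 205.5/144) = 85.08, rounded up to 86. The stated 86 reproduces, and 86 + 14 = 100. The 16% and the 5-point margin serve as yardsticks below.

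**2. Timing.** Hi-VNI begins after induction and the mask trial (3.3). Section 5.4 allows discontinuation before or during surgery, so its wording covers the period after the start.

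**3. Direction.** Let s be completers per 100 started and w the discontinued non-completers left out.

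Reported rate = s / (100 − w), against s / 100 if all are kept.

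The numerator is unchanged and the denominator shrinks, so the reported rate is higher whenever s and w are above zero. Dropping a completer would lower it (15/99 = 15.2%), but someone taken off as a poor candidate for Hi-VNI during surgery is not a completer.

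**4. Size.** The documents do not give w, so every non-zero value is an assumption. The 50% rate is also an assumption.

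| w per 100 started | True rate 16% (plan) | True rate 50% (assumed) |
|---|---|---|
| 0 | 16.0% | 50.0% |
| 5 | 16.8% | 52.6% |
| 10 | 17.8% | 55.6% |
| 14 | 18.6% | 58.1% |
| 20 | 20.0% | 62.5% |
| 24 | 21.1% | 65.8% |

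The value 14 borrows the whole allowance in 6.1. It is a high case for that allowance, which also covers non-consent.

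**5. Against the 5-point margin.** At 16%, 23 removals give 16/77 = 20.8% and 24 give 16/76 = 21.1%. It therefore takes 24 of the 84 failures (28.6%) to exceed the margin. At 50%, 9 removals give 50/91 = 54.9% and 10 give 50/90 = 55.6%, so 10 of the 50 failures (20%) are enough.

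**6. Against sampling error.** The exact 95% interval is 9.4% to 24.7% for 16/100 and 11.0% to 28.4% for 16/86. The 2.6-point shift is small beside either width.

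**The case against.** The strongest reply is that the protocol never says these subjects leave the denominator, and that several sections lean towards keeping them. Section 3.4.1 assesses the endpoint in each case. Section 3.1 looks for suitable scenarios among the cases that were completed without an adjunct, which implies that the sample also holds cases that were not. Section 3.3 expects some study cases in which Hi-VNI alone is not enough. Section 5.5 says that everything captured will contribute. The mandated switches cover the main failures without removing anyone, and the 16% planning rate makes sense only if those conversions count as non-completions.

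Timing is also less clear-cut than it looks. The protocol does not define when the procedure begins. Section 5.1 puts the mask check at the beginning of the case, 3.4.2 counts case duration from induction, and 10.1 calls failed mask ventilation a withdrawal. Some discontinuations under 5.4 may therefore be that exclusion before the start.

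Finally, this is a pilot with no comparator and no stated success threshold, so no decision rule would be overturned.

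Most of this stands, and it limits the point. It does not close the gap. None of these sections says how a discontinued subject is counted, 5.4 is not confined to events before the start or to late-found ineligibility, and leaving the study is the phrase's natural meaning. Section 8.1 keeps data usable after authorization is revoked, so records need not be lost; the open question is the denominator.

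**Conclusion.** The point holds as a gap in the analysis rules. Section 5.4 permits removal that can depend on outcome, after Hi-VNI has started, and no visible text keeps those subjects in the primary denominator. The schedule of events and two figures are not shown in the available text.

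A reader might infer that the completion rate is bound to be biased upward, or that the plan removes Hi-VNI failures. The documents support neither. Only the direction is settled, and only if discontinued non-completers are dropped. Whether they would be dropped is not stated, and how many there would be is unknown.

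At the planned 16% the effect is modest: 18.6% with 14 removed, and 24 removals needed to pass the 5-point margin. It grows with the true rate, reaching 55.6% with 10 removed at an assumed 50%, so it matters mainly if Hi-VNI does much better than planned. It should be fixed because the remedy is cheap and the rate is the primary result.

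**What to change.** Change the analysis text only; clinical discretion to stop Hi-VNI stays as it is.

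1. In 6.3.2, define the primary analysis set as all consented patients in whom Hi-VNI was started.
2. Keep every such patient in the denominator. Count any switch to another mode, investigator discontinuation or abort before the end of the procedure as not completed on Hi-VNI alone, and tabulate the reasons.
3. Add a sensitivity analysis that leaves out purely surgical aborts and subjects found ineligible after the start.
4. Report exclusions before the start (failed mask ventilation, pre-operative withdrawal) as separate counts.
5. In 6.1, limit the 14-patient allowance to losses before Hi-VNI starts.

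The cost is a few sentences. Non-completion is known at the moment of discontinuation, and 5.2 already plans recording in surgery and in the recovery unit, so no new measurement is needed beyond noting the reason. The drawbacks are that the reported rate may be slightly lower and that a few subjects found ineligible late count as non-completions in the primary analysis; item 3 shows how much that matters.
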